Walsh, Z. et al. (2013). Cannabis for therapeutic purposes: patient characteristics, access, and reasons for use. *Int J Drug Policy* 24(6), 511-516

Zhornitsky, S., & Potvin, S. (2012). Cannabidiol in humans – the quest for therapeutic targets.

Zuardi, A.W. et al. (2009). Cannabidiol for the treatment of psychosis in Parkinson's disease. *Journal of Psychopharmacology*, 23, 979-983

Statistical Approaches

All statistical analyses will be conducted using IBM SPSS Statistics (version 25). Data will be screened for outliers (defined as outside 1.5x the interquartile range), skew, kurtosis, non-normality, and homogeneity of variance. If the assumptions of parametric inferential analyses are not met, the appropriate non-parametric analyses will be performed. Baseline demographic, clinical, and neuropsychological data will be assessed using 2-tailed analyses of variance (ANOVAs). Treatment effects over the course of the study will be assessed using mixed model ANOVAs with Scheffe post hoc tests utilized to assess between-group differences and Least Significant Difference (LSD) post hoc tests utilized to assess change over time (repeated-measures). Independent *t*-tests will be conducting for each individual treatment arm to assess post hoc differences between baseline data relative to post-treatment data. In order to observe small-to-medium effect interaction effect sizes ($f=.20$) with 85% statistical power with alpha set at .05, it is estimated that the sample size should be at least 45 participants.

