In order to assess the efficacy of the dose chosen for the double-blind study, we will also conduct a small open-label phase I trial of the full-spectrum CBD tincture prior to initiating the double-blind study. This open-label trial will enroll up to 22 participants who are interested in using CBD, and who have anxiety. This trial will determine whether patients derive clinical benefits at the current dosage proposed for the active treatment arm of the double-blind trial. This trial will examine all components of the originally proposed study. During the open-label phase, a subset of participants (up to n=16) will complete an extra visit that includes clinical rating scales and a 2-hour continuous blood draw directly following administration of the tincture in order to assess plasma concentration of CBD over time and correlation with anxiety.

Subjects will be recruited through IRB-approved advertisements and flyers in regions that have approved medical marijuana. Additionally, medical marijuana healthcare facilities throughout New England, including CannaCare, Integr8, MMJ Physician Practice, and others, may also refer interested patients to contact the study recruitment line for further screening. These healthcare groups provide their interested patients who meet for general inclusion criteria with study recruitment materials. The total sample size for the double-blind study is 75 (45 full-spectrum CBD, 15 single-compound CBD, and 15 placebo); up to 15 of each group (45 total) will also complete the MRI scanning protocol. For the open-label trial, the total sample size is 16 (we will enroll up to 22 to ensure 16 completers); up to 16 subjects will complete the MRI scanning protocol.

Inclusion Criteria

- 1) Subject has provided informed consent
- 2) Subject is 18 or older
- 3) Subject is a native English speaker or acquired English prior to age 5
- 4) Subject scores a minimum of 16 on the Beck Anxiety Inventory (BAI) OR a minimum of 11 on the Overall Anxiety Severity and Impairment Scale (OASIS) at the screening/baseline visit or at phone screening if within 2 weeks of the baseline visit

Exclusion Criteria

Subjects will be excluded if they report any of the following:

- 1) Non-native English speakers
- 2) Estimated IQ < 75
- 3) Meets criteria for DSM-V classification of current substance abuse/dependence, a psychotic disorder, bipolar disorder, or an eating disorder

- 4) A history of head injury or loss of consciousness greater than 5 minutes

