A subset of patients in the open-label phase (up to n=16) will complete an optional 6th visit at least one week after completing the open-label phase of the clinical trial. At this visit, an intravenous catheter will be inserted in an antecubital vein for withdrawal of blood samples for subsequent measure of blood CBD and THC levels. The catheter will be inserted 5 to 10 minutes before the sublingual administration of the standard dose of full-spectrum CBD tincture (1mL of 10mg/ml CBD). Blood will be drawn at a maximum rate of 1 mL/min, and five (5) minute samples will be drawn from 5 to 90 minutes after tincture administration and every 10 minutes from 90 to 120 minutes. Quantitative analyses of CBD and THC levels will be performed by gas chromatography. A total of less than 120 mL of whole blood will be drawn on the study day. This method of continuous sampling has been in place and used successfully in [name] laboratory since 1986 (including current approved protocol [REDACTED]).

A subset of patients in the double-blind phase (up to n=75) will complete a blood draw at baseline and week 4. Plasma will be analyzed for circulating levels of endocannabinoids, including: AEA, 2-AG, 2-OG, PEA, and OEA. Levels of cortisol will also be analyzed. Approximately 10ml of whole blood will be drawn into a non-heparinized tube, centrifuged to separate the plasma, flash frozen and transported to [REDACTED]. The samples will be analyzed via mass spectrometry and levels of each endocannabinoid will be assessed pre- and post-CBD treatment.

For the double-blind study, at the end of the baseline visit, eligible subjects will be randomized to either full-spectrum CBD, single-compound CBD, or placebo using a standard 3:1:1 randomization procedure. In the open-label trial, all subjects will be provided with the full-spectrum CBD tincture at the conclusion of the baseline visit. Subjects will be instructed on how to administer the compound in the morning, midday, and evening; they will be instructed how to draw one full dropper of compound, deposit the amount in the dropper under the tongue, hold for 45-60 seconds, then swallow.

For studies involving treatment or diagnosis, provide information about standard of care at Partners (e.g., BWH, MGH) and indicate how the study procedures differ from standard care. Provide information on available alternative treatments, procedures, or methods of diagnosis.

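### Baseline data are significance-tested after randomisation, while no between-arm analysis uses the baseline score as a covariate, so precision is lost

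*Combined protocol and SAP*

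**What the plan says.** The Statistical Approaches section at the end of the combined protocol and SAP covers both baseline data and treatment effects.

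- Baseline: "Baseline demographic, clinical, and neuropsychological data will be assessed using 2-tailed analyses of variance (ANOVAs"). It does not say what would follow from a significant result.
- Treatment effects: "Treatment effects over the course of the study will be assessed using mixed model ANOVAs with Scheffe post hoc tests utilized to assess between-group differences", with LSD tests for change over time.
- Within arms: t-tests "for each individual treatment arm to assess post hoc differences between baseline data relative to post-treatment data".

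The section names neither ANCOVA nor any covariate, and the rest of the document does not supply one.

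Under Research Design and Methods, the timing is that "at the end of the baseline visit, eligible subjects will be randomized to either full-spectrum CBD, single-compound CBD, or placebo", in a 3:1:1 ratio with no stratification factor named. The planned size is "The total sample size for the double-blind study is 75 (45 full-spectrum CBD, 15 single-compound CBD, and 15 placebo"). Clinical scales are completed at baseline and at each weekly visit. Neuropsychological tests and, in subsets, MRI and endocannabinoid levels are taken only at baseline and week 4. MRI is limited to 15 people per group.

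**The concern.** The baseline data are collected before allocation, so under proper randomisation the null hypothesis of the baseline ANOVAs is true by design. A significant result is a false alarm. A non-significant one says little, because two of the three arms have 15 people and every placebo comparison involves one of those arms.

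The baseline score is the obvious covariate for each outcome and is already collected, but the plan does not use it as one. In a mixed ANOVA with baseline as a level of time, baseline enters only through change. A change score subtracts the whole baseline difference, although only the fraction rho of it is expected to persist to week 4. It therefore over-corrects a chance imbalance and carries more noise than it needs to. With a placebo group of 15, that precision is worth having.

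**Working it through.** **Inputs from the documents.** Arms of 45, 15 and 15; five visits; Scheffe for between-group differences; alpha .05.

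**Assumptions.** The correlation rho between baseline and week 4 (range .3 to .8), an illustrative true effect of 0.6 SD, equal SDs at both visits, and complete data on all 75. None of these is in the documents.

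**The plan's own figure.** The section seeks an interaction of f = .20 "with 85% statistical power with alpha set at .05" and concludes that "it is estimated that the sample size should be at least 45 participants". For a within-between interaction with k = 3 arms and m = 5 visits:

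- lambda = f²·N·m/(1-rho), df1 = (k-1)(m-1), df2 = (N-k)(m-1).
- At rho = .5 with sphericity and N = 45: lambda = .04 × 45 × 5/.5 = 18, df = 8 and 168, power 86.1%.
- The minimum N is 44, or 45 in three equal arms.

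The stated figure therefore reproduces, on assumptions the plan leaves unstated. It refers to the interaction test, not to a baseline-adjusted comparison.

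**Chance baseline imbalance.** In SD units, the difference between two arms has standard error sqrt(1/n1 + 1/n2).

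- 45 v 15: sqrt(1/45 + 1/15) = 0.298. P(|D| > 0.3) is about 31%; P(|D| > 0.5) is about 9%.
- 15 v 15: sqrt(2/15) = 0.365. P(|D| > 0.3) is about 41%.

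In simulated randomisations at 45/15/15, the three-arm baseline ANOVA was non-significant in about 88% of trials where full-spectrum and placebo differed by more than 0.3 SD. Where they differed by more than 0.5 SD, it was non-significant in about 70%.

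**Conditional shift, two-visit outcomes.** Given D, the expected week-4 difference is effect + rho·D. The expected difference in change is effect + rho·D - D = effect - (1-rho)D. For D = 0.5 SD the shift is 0.35/0.25/0.15 SD at rho .3/.5/.7. Baseline as a covariate removes it under a linear model.

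**Precision, two-visit outcomes.** With unit SD, the variance is 2(1-rho) for change and 1-rho² for the adjusted analysis. The ratio is (1-rho²)/(2(1-rho)) = (1+rho)/2, which is below 1 for every rho below 1.

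**Power, 45 v 15, 0.6 SD.** The Scheffe critical value is sqrt(2 × F(.95; 2, 72)) = sqrt(2 × 3.12) = 2.50. The non-centrality is 0.6/(0.298 × sqrt(variance)). At rho = .5 this is 2.01 for change and 2.32 adjusted. Power comes from the non-central t with 72 df (change) or 71 df (adjusted).

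| Assumed rho | Variance ratio | Change score | Baseline-adjusted |
|---|---|---|---|
| .3 | .65 | 22% | 35% |
| .5 | .75 | 32% | 44% |
| .6 | .80 | 41% | 51% |
| .7 | .85 | 54% | 63% |
| .8 | .90 | 75% | 80% |

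For 15 v 15 at rho .5/.6/.7, power goes from 20/26/36% to 28/33/43%.

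**Scope.** The identity with change scores holds for two-visit outcomes. For the weekly scales, the five-visit interaction is not a single change score, and no power figure is claimed for it. The 45 v 15 figures cannot apply to MRI.

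**The case against.** The strongest reply is that the plan is valid as it stands. Randomisation keeps a change-score comparison unbiased on average, and a mixed ANOVA with baseline as a time level does use the baseline data. That stands: what is lost is precision and protection against the imbalance that happens to occur, not validity.

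Several stronger readings are tempting but not supported.

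- A reader might infer that imbalance would go unnoticed. A non-significant test does not hide the arm means, and the plan attaches no decision to the test.
- A reader might infer that the baseline score is ignored. It enters through change, which is inefficient. That baseline is a time level is itself implied rather than stated.
- A reader might infer that only a very large imbalance could reach significance. It depends on the pattern. If the full-spectrum arm differs from both small arms, an observed difference of sqrt(2 × 3.12/18) = 0.59 SD is enough (18 = 45 × 30/75).
- A reader might want current medication as a further covariate. Participants do keep their existing treatment, but the plan lists no medication variable for analysis and gives no evidence of its prognostic value.

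It is also fair to say that the gain depends on an unknown rho. At rho = .8 the variance saving is only 10%. The plan also does not say to which contrast the Scheffe test is applied; the power figures here apply it to the week-4 comparison. An unadjusted t-test would give higher absolute power (51/60/73% rising to 63/70/79%), but it is not the planned between-group test.

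**Conclusion.** The point holds as a matter of efficiency and of sensitivity to chance imbalance. The baseline ANOVAs answer no useful question after randomisation. The missing baseline covariate costs 10 to 35% of the change-score variance for two-visit outcomes over rho .8 to .3. In the 45 v 15 comparison, that is about 9 to 12 percentage points of power at rho .5 to .7 for a 0.6 SD effect. A 0.5 SD imbalance, expected in about 9% of trials for that pair, would move a change-score contrast by 0.15 to 0.25 SD at rho .7 to .5. The direction of the gain holds for every rho below 1 under a linear model with equal SDs. Its size rests on the assumed rho, effect and complete data. The change is worth making before unblinding, but the plan is not invalid without it.

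**What to change.** 1. Replace the baseline sentence with a statement that baseline data will be summarised by arm (mean and SD, or count and percentage) without significance tests.
2. In every between-arm comparison, analyse post-baseline values with the baseline value of the same outcome as covariate. Use ANCOVA at week 4 for cognition, MRI and endocannabinoids. For the weekly scales, model weeks 1 to 4 with baseline as covariate and take baseline out of the time factor.
3. Reword the sample-size sentence to name the test it now refers to, because the stated 45 was derived for an interaction effect. Give the assumed correlation alongside it.

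The cost is one degree of freedom per model and a revision of the Statistical Approaches section, including a check of the sample-size statement. No new data or visits are needed, since the baseline scores are already collected.

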Despite the recent interest in cannabinoid-based products, no published studies to date have conducted a clinical trial of products high in CBD in individuals who suffer from anxiety. Further, none have systematically evaluated baseline and follow-up clinical state and related quality of life measures in individuals taking CBD, or assessed measures of brain structure and function before and after treatment with CBD using neuropsychological measures or neuroimaging. As a growing number of states are legalizing medical marijuana and increasing evidence suggests that CBD may exert anxiolytic effects, there is a gap in the literature regarding the effects of CBD, often found in higher levels in medical marijuana than recreational marijuana, on anxiety. This investigation will be the first of its kind to conduct a double-blind clinical trial of high-CBD compounds (both full-spectrum and single-compound) in individuals with anxiety. The main outcome measures of the project will include a comprehensive assessment of anxiety using both self-report and administered scales pre- and post-treatment, as well as range of quality of life measures. In addition, this project will examine the impact of high CBD products relative to placebo on several cognitive domains using neuropsychological testing. Furthermore, a subset of eligible participants will complete a structural and functional MRI scanning to assess brain function and connectivity using a multimodal neuroimaging protocol prior to and following four weeks of treatment with high CBD compounds vs placebo.

RESEARCH DESIGN AND METHODS

Briefly describe study design and anticipated enrollment, i.e., number of subjects to be enrolled by researchers study-wide and by Partners researchers. Provide a brief summary of the eligibility criteria (for example, age range, gender, medical condition). Include any local site restrictions, for example, "Enrollment at Partners will be limited to adults although the sponsor's protocol is open to both children and adults."

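### The only pairwise between-arm procedure the plan names is not tied to a week-4 contrast with placebo, and on its natural reading it averages in the pre-randomisation baseline visit

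*Combined protocol and SAP*

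**What the plan says.** Statistical Approaches assigns a procedure to each kind of comparison:

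- Between arms: "Treatment effects over the course of the study will be assessed using mixed model ANOVAs with Scheffe post hoc tests utilized to assess between-group differences".
- Over time: "Least Significant Difference (LSD) post hoc tests utilized to assess change over time (repeated-measures").
- Within an arm: t-tests "for each individual treatment arm to assess post hoc differences between baseline data relative to post-treatment data".

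The sample-size sentence then refers to an interaction effect of f = 0.20, "with 85% statistical power with alpha set at .05", and concludes that "it is estimated that the sample size should be at least 45 participants". The word interaction occurs nowhere else in the section. No primary time point, baseline adjustment or named contrast with placebo is given.

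Background and Significance promises comparisons with placebo, for example: "this project will examine the impact of high CBD products relative to placebo on several cognitive domains using neuropsychological testing". Under Research Design and Methods, the clinical scales are taken at five visits (baseline and weeks 1 to 4) and the neuropsychological tests at two (baseline and the final visit). Randomisation comes at the end of the baseline visit. The double-blind sample is 75: 45 full-spectrum, 15 single-compound and 15 placebo.

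**The concern.** In a group-by-time ANOVA, a post hoc test on the between-subject factor compares arm means pooled over every level of time. If baseline is one of those levels, the pooled mean includes a visit at which the expected difference between arms is zero, because nobody has yet been randomised. The result is not the treatment effect at the end of treatment. It is a smaller quantity whose size depends on how fast the effect appears.

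The other named tests do not fill the gap. LSD and the t-tests look at change within an arm or over time. The interaction does compare change between arms, but with three arms it is an omnibus test: (3 − 1) × (5 − 1) = 8 numerator degrees of freedom for the weekly scales and (3 − 1) × (2 − 1) = 2 for the cognitive tests. At stake is whether the trial can say how far each CBD product differs from placebo after four weeks.

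**Working it through.** **1. The plan's own figure.** For the within-between interaction of a repeated-measures ANOVA with k arms and m visits, λ = f²·N·m/(1 − ρ), df1 = (k − 1)(m − 1) and df2 = (N − k)(m − 1). The plan gives f = 0.20, alpha 0.05 and 85% power. I assume k = 3 equal arms, m = 5, ρ = 0.5 and sphericity. At N = 45, λ = 0.04 × 45 × 5/0.5 = 18.0 with 8 and 168 df, and power is 86.1%. The smallest N reaching 85% is 44, or 45 in three equal arms. So the stated figure reproduces as an interaction. It is sensitive to ρ: with five visits, 61 at ρ = 0.3, 36 at 0.6 and 28 at 0.7. With two visits, ρ = 0.7 also gives 45. A group main effect with the same f, k, m and ρ = 0.5 would need 167. The trial is therefore sized on an interaction, while the named pairwise procedure, read as a test on the group factor, addresses a main effect.

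**2. Dilution.** The pooled difference equals the week-4 difference D times the mean of the onset profile, with baseline at 0. The documents give no onset pattern, so these are assumed:

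| Visits and onset (share of D) | Pooled difference |
|---|---|
| Two visits: 0, 1 | 0.50 D |
| Five, linear: 0, .25, .5, .75, 1 | 0.50 D |
| Five, early: 0, .5, .75, .9, 1 | 0.63 D |
| Five, full from week 1: 0, 1, 1, 1, 1 | 0.80 D |
| Five, late: 0, 0, 0, .5, 1 | 0.30 D |

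**3. Power, full-spectrum v placebo (45 v 15).** Assumed: D = 0.8 SD, ρ = 0.5. The SD of a participant's mean over m visits is √((1 + (m − 1)ρ)/m), which is √0.75 = 0.866 for two visits and √0.6 = 0.775 for five. The noncentrality is the standardised difference divided by √(1/45 + 1/15) = 0.298. The Scheffe critical value is √(2·F(0.95; 2, 72)) = 2.50. The Dunnett value, simulated for 45/15/15, is 2.24.

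| Contrast | Standardised difference | Power |
|---|---|---|
| Pooled, two visits, Scheffe | 0.40/0.866 = 0.46 | 18% |
| Pooled, five visits, linear, Scheffe | 0.40/0.775 = 0.52 | 23% |
| Pooled, five visits, early, Scheffe | 0.504/0.775 = 0.65 | 38% |
| Pooled, full from week 1, Scheffe | 0.64/0.775 = 0.83 | 61% |
| Week 4 or change score, unadjusted, Scheffe | 0.80 | 57.5% |
| Week 4 adjusted for baseline, Scheffe | 0.8/√(1 − 0.25) = 0.92 | 72% |
| Week 4 adjusted for baseline, Dunnett | 0.92 | 80% |

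For single-compound v placebo (15 v 15), Scheffe power is 14.6% on pooled means with linear onset and 51.5% for the baseline-adjusted week-4 contrast.

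**4. Sensitivity to ρ (45 v 15, D = 0.8, Scheffe throughout).**

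| ρ | Two visits | Five, linear | Full from week 1 | Adjusted week 4 |
|---|---|---|---|---|
| 0.3 | 21% | 32% | 77% | 62% |
| 0.5 | 18% | 23% | 61% | 72% |
| 0.7 | 16% | 18% | 49% | 89% |

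At ρ = 0.3 with the full effect from week 1, pooling loses no power, because averaging five visits lowers the SD. The estimate is still 20% below the week-4 difference.

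**The case against.** The strongest reply is that the text never says Scheffe is run on visit-averaged means. Applying it at each visit or to change scores also fits the words. That stands: the pooled reading is an inference. It is the natural one, because the sentence gives Scheffe to groups and LSD to time. If it is not what is meant, the plan names no pairwise contrast with placebo at all, and the visit and metric remain open.

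A reader might also infer that the plan contains no other comparison between arms. The documents do not support that. The sample size rests on an interaction, which tests differential change and is not diluted by baseline. At D = 0.8 and ρ = 0.5 with 45/15/15, it has about 55% to 77% power for five visits with linear onset and 68% to 85% for two visits. The lower figure applies if both products work equally and the higher if only full-spectrum works. What remains is that it is omnibus and is not named as the test of treatment.

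Nor may one infer that effects of the planned size would mostly be missed. D = 0.8 is an assumption, and over five visits with linear onset it corresponds to an interaction f of about 0.11 to 0.14, below the plan's 0.20. At f = 0.20 and ρ = 0.5, Scheffe power on pooled means for 45 v 15 is 50% to 71% (linear) or 85% to 96% (full from week 1). Only two-visit outcomes stay low, at 19% to 29%.

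Finally, Scheffe is valid and controls family-wise error. Preferring Dunnett is a choice about power, not a correction.

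**Conclusion.** The point holds in a conditional form. The plan names one pairwise between-arm procedure, does not define what it is applied to, and specifies no baseline-adjusted week-4 contrast of either CBD product with placebo. On the natural reading, the estimate is diluted whatever the onset: exactly by half for outcomes measured at baseline and week 4 only, and by 20% to 70% for weekly scales across the patterns examined. A flat statement that the effect is halved would be right only for two-visit outcomes and linear onset.

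The power figures rest on assumed values of D, ρ and onset, none of which the documents give. The gap between 23% and 80% combines three changes: time point, baseline adjustment and multiplicity method. With Scheffe kept, the comparison is 23% against 72%, so most of the gain comes from the contrast. The case is firmest for the cognitive outcomes, where the halving depends on no onset assumption.

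**What to change.** State in Statistical Approaches that the treatment effect is the difference in week-4 score, adjusted for baseline, for full-spectrum v placebo and for single-compound v placebo. Estimate it from a model of the post-baseline visits with arm, visit, arm-by-visit and baseline score as covariate. For outcomes measured only at baseline and week 4, use ANCOVA. Name the multiplicity adjustment for the two comparisons: Scheffe may stay, and Dunnett is an optional gain in power. State that visit-averaged group means which include baseline are not the treatment comparison, and that within-arm tests are descriptive.

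The cost is SAP wording and a different procedure in the software already planned (SPSS MIXED or UNIANOVA). It uses data the trial already collects and needs no extra visits or participants.
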